6. OTHER ENDPOINTS

Palatability and Acceptability of selexipag

Palatability and Acceptability of selexipag formulation will be assessed.

Answers for each question in the palatability questionnaire for Caregivers/Site Personnel, assessed via 5-point facial hedonic scale, will be summarized with counts and percentages by timepoint.

Acceptability of the selexipag formulation will be assessed through a 3-point categorical scale as to whether the child swallowed the medication at visits indicated in the assessment schedule: for all participants, parent(s) or LAR(s) or study site personnel will be asked following the drug intake whether the child swallowed the medication:

- a. fully,
- b. partially,
- c. not at all.

Answers for each question in acceptability questionnaire will be summarized with counts and percentages by timepoint.

Palatability and acceptability will also be listed.

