#### 6.4 Other endpoints

- Palatability of selexipag formulation at Day 1, Week 12, and EOT, assessed using a 5-point facial hedonic scale.

- Acceptability of selexipag formulation at Day 1, Week 12, and EOT, as assessed through a 3-point categorical scale as to whether the child swallowed the medication.

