#### 7.2.2.6 Palatability and acceptability

The palatability of the selexipag formulation will be assessed at the visits indicated in the assessment schedule using a 5-point facial hedonic scale.

For children not able to comply with the instructions of the test, palatability will be indirectly assessed by the participant's parent(s) or LAR(s) or study site personnel [see Section 14.3 Appendix 3].

The site study personnel will record the palatability score corresponding to the smiley face pointed to by the participant or the response provided by participant's parent(s) or LAR(s) or study site personnel in the eCRF.

The acceptability of the selexipag formulation will be assessed through a 3-point categorical scale as to whether the child swallowed the medication at the visits indicated in the assessment schedule.

For all participants, parent(s) or LAR(s) or study site personnel will be asked, following the study drug intake, whether the child swallowed the medication:

- a. fully,
- b. partially,
- c. not at all.

The site study personnel will record the acceptability score corresponding to the response provided by participant's parent(s) or LAR(s) or study site personnel in the eCRF and source documents.

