##### **10.3.7.1 Palatability and acceptability**

The palatability and acceptability of selexipag will be summarized separately with counts and percentages.

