- Class I Asymptomatic, growing along own centiles, attending school regularly, no limitation of physical activity, playing sports with his/her classmates.
- Class II Slight limitation of physical activity, unduly dyspnoeic and fatigued when playing with his/her classmates. Comfortable at rest. Continues to grow along own centiles. School attendance 75% normal. No chest pain.
- Class IIIa Marked limitation of physical activity. No attempt at sports. Comfortable at rest. Less than ordinary activity causes undue dyspnea, fatigue, syncope, or chest pain. Schooling compromised < 50% normal attendance.
- Class IIIb Unable to attend school, but mobile at home and interacting with friends. Wheelchair needed outside the home. Growth compromised. Poor appetite. Supplemental feeding. Less than ordinary activity (eg, dressing) causes undue

dyspnea, fatigue, syncope and/or presyncope, or chest pain. Plus features of Class IIIa.

Class IV Unable to carry out any physical activity without undue dyspnea, fatigue, syncope, or chest pain, unable to attend school, wheelchair dependent, not interacting with friends. Syncope and/or right heart failure. Plus features of Class III.

**14.3 Appendix 3 Palatability And Acceptability Of Selexipag  
PALATABILITY QUESTIONNAIRE FOR SUBJECTS**

1.	How much do you like the taste of this medicine?	
  
 1	2	3	4	5	
   
 					
 
 Dislike very much	Dislike a little	Not sure	Like a little	Like very much	
  
	1	2	3	4	5						Dislike very much	Dislike a little	Not sure	Like a little	Like very much
1	2	3	4	5													
																	
Dislike very much	Dislike a little	Not sure	Like a little	Like very much													
2.	How easily can you swallow this medicine?	
  
 1	2	3	4	5	
   
 					
 
 Very difficult	Difficult	OK	Easy	Very easy	
  
	1	2	3	4	5						Very difficult	Difficult	OK	Easy	Very easy
1	2	3	4	5													
																	
Very difficult	Difficult	OK	Easy	Very easy													

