3.	How much do you like that this medicine is taken twice every day?	
  
 1	2	3	4	5	
   
 					
 
 Dislike very much	Dislike a little	Not sure	Like a little	Like very much	
  
	1	2	3	4	5						Dislike very much	Dislike a little	Not sure	Like a little	Like very much
1	2	3	4	5													
																	
Dislike very much	Dislike a little	Not sure	Like a little	Like very much													
4.	How easy is it to remove the medicine from the packaging?	
  
 1	2	3	4	5	
   
 					
 
 Very difficult	Difficult	OK	Easy	Very easy	
  
	1	2	3	4	5						Very difficult	Difficult	OK	Easy	Very easy
1	2	3	4	5													
																	
Very difficult	Difficult	OK	Easy	Very easy													

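### Three descriptive SAP rules are wrong or incomplete as written: self-rated palatability is not tabulated, time since diagnosis and first symptoms is subtracted in reverse, and the NT-proBNP log step is missing

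*SAP*

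**What the plan says.** **Palatability.** Protocol 6.4 names the endpoint: "Palatability of selexipag formulation at Day 1, Week 12, and EOT, assessed using a 5-point facial hedonic scale". Protocol 7.2.2.6 describes self-rating first: "The site study personnel will record the palatability score corresponding to the smiley face pointed to by the participant". A proxy is the exception: "For children not able to comply with the instructions of the test, palatability will be indirectly assessed by the" parents, legal representatives or site staff. Protocol Appendix 3 (Section 14.3) prints two forms. The first is headed "PALATABILITY QUESTIONNAIRE FOR SUBJECTS" and the second is for caregivers and site personnel. Protocol 10.3.7.1 gives the analysis: "The palatability and acceptability of selexipag will be summarized separately with counts and percentages". SAP 6, by contrast, plans this at each visit where palatability is assessed: "Answers for each question in the palatability questionnaire for Caregivers/Site Personnel, assessed via 5-point facial hedonic scale, will be summarized with counts and percentages". It adds that palatability will be listed and says nothing about tabulating the subject form.

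**Disease duration.** SAP 3.1 defines time from PAH diagnosis as the diagnosis date minus the screening date plus 1. It defines time from first observed or assumed symptoms in the same way.

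**NT-proBNP.** Protocol 10.3.6.5 summarises percent of baseline on the log scale, then exponentiates the mean and 95% CI to give a geometric mean. SAP 5.2.3 keeps the exponentiation and the geometric-mean label but does not say that the statistics are computed on logs.

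**The concern.** Each of these is a stated rule that gives an incomplete or wrong output if a programmer follows it literally.

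Palatability is the substantive item. The protocol puts the child's own answer first, and the SAP's only palatability table is built from the fallback rater. SAP 7 also requires categorical summaries to account for everyone in the analysis set and to show how many have missing data. A child who rated the medicine personally, and so has no caregiver form, could therefore be shown as missing although a score was recorded.

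The other two are drafting slips. Disease duration would print as zero or negative, with the minimum and maximum exchanging meaning. The NT-proBNP geometric mean could not be produced from the SAP text alone.

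**Working it through.** The plan states no sample size, power or error rate for these items, so there is no planned figure to reproduce. The check compares the texts and applies two SAP rules literally to illustrative values, which are assumptions and not trial data.

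**1. Palatability**

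| Question | Protocol | SAP 6 |
|---|---|---|
| Who rates? | The child; a proxy if the child cannot follow the test (7.2.2.6) | Names the caregiver/site form only |
| Forms available | Subject form and caregiver/site form (Appendix 3) | One of the two |
| Output | Counts and percentages, no limit by respondent (10.3.7.1) | Counts and percentages for the caregiver/site form; listing for palatability generally |

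Could the SAP assume that caregivers answer for every child? Protocol 7.2.2.6 does put a question to adults about everyone, "For all participants, parent(s) or LAR(s) or study site personnel will be asked, following the study drug intake, whether the child swallowed the medication", but that is the acceptability question. It does not extend to palatability.

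The two forms are not fully interchangeable. Item 3 of the subject form asks the child, "How much do you like that this medicine is taken twice every day"; item 3 of the caregiver form asks for the caregiver's own liking of giving it twice daily. Item 4, on packaging, is worded identically on both.

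**2. Time from diagnosis and from first symptoms**

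The SAP formula is event date - screening date + 1. With the dates swapped and the plus 1 kept, it is screening date - event date + 1.

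| Event before screening (days) | SAP as written | Dates swapped |
|---|---|---|
| 0 | 0 + 1 = 1 | 0 + 1 = 1 |
| 1 | -1 + 1 = 0 | 1 + 1 = 2 |
| 365 | -365 + 1 = -364 | 365 + 1 = 366 |
| 730 | -730 + 1 = -729 | 730 + 1 = 731 |

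Inclusion criterion 3 rests on a historical catheterization before enrolment, so diagnosis will normally precede screening and the negative rows are the usual case. Besides the sign, the plus 1 now shortens the magnitude by a day where it should count inclusively. In a summary table the printed minimum would be the longest disease duration.

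**3. NT-proBNP percent of baseline**

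Assume five values: 50, 70, 80, 100 and 150.

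- SAP text taken literally: the arithmetic mean is 450/5 = 90, and exp(90) is about 1.2 x 10^39. This is not a geometric mean.
- Protocol text: the mean of the logs is 4.432, and exp(4.432) is about 84.1%. With a log-scale SD of 0.410, the standard error is 0.410/√5 = 0.183. With t = 2.776 on 4 degrees of freedom, the 95% CI is exp(4.432 ± 2.776 × 0.183), or 50.6% to 139.8%.

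**The case against.** **Nothing is lost.** The SAP lists palatability without restricting the respondent, the protocol still calls for a summary, and SAP 2.3 leaves output detail to a Data Presentation Plan that is not among the documents and may include the table. This stands as a limit: a reader might infer that children's ratings are discarded, or that the SAP deliberately narrowed the endpoint to caregivers, and the documents support neither. A listing is still not the summary that Protocol 10.3.7.1 describes.

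**The gap can be sized from the cohorts.** A reader might take planned enrolment of about 20 per cohort and conclude that one third or two thirds of children would be left out. That requires whole cohorts to self-rate or not, which the documents nowhere say. They give no share.

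**Negative days are already a SAP convention.** SAP 7 does give negative Study Days to dates before treatment start. That rule has a different reference date, uses elapsed days and never yields 0, whereas the SAP 3.1 formula gives 0 for the day before screening. Nor does a negative value fit a variable labelled as time since an event. The objection is right that no new day-count decision is needed, because SAP 3.1 already specifies plus 1.

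**The NT-proBNP intent is obvious.** It is: an inverse transformation to a geometric mean presupposes logs, and the protocol says so. A reader might infer a change of method, or expect a figure such as 10^39 to be reported; neither is plausible. The SAP's general laboratory summaries do not fill the gap, since they cover values and changes, while the endpoint is percent of baseline.

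**Conclusion.** The point holds as a minor one. Three descriptive SAP rules need correction, and none bears on the primary PK endpoint, dose confirmation or sample size.

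Palatability is the only real departure from the protocol: self-rated answers are listed but have no table in the SAP, and could be counted as missing. Confidence is high about the SAP wording and lower about the eventual output, because the Data Presentation Plan has not been seen. The number of children affected is unknown.

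The two date formulas give the wrong sign and a magnitude one day short for any event before screening (two days short of the inclusive count). The NT-proBNP sentence cannot be executed as written, although its meaning can be recovered. Both would probably be noticed on first output.

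**What to change.** - **SAP 6:** also tabulate the subject palatability questionnaire, with counts and percentages by timepoint. Labelling results by respondent is advisable because item 3 differs between the forms, but no section requires it, and splitting gives smaller denominators.
- **SAP 3.1:** swap the dates in both formulas and keep the stated plus 1, that is, screening date minus event date plus 1.
- **SAP 5.2.3:** restore the log step. Compute the mean and 95% CI on the log of percent of baseline, then exponentiate.

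The cost is four small text edits (one sentence in SAP 6, two formulas in SAP 3.1, one phrase in SAP 5.2.3) and one extra table. No new data are needed, since the protocol already has site staff record the child's score in the eCRF.

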7. STATISTICAL METHODS, CONVENTIONS FOR DISPLAYS AND DECIMAL PRECISION

Unless otherwise specified, all listings will be provided by center and participant number within each age cohort. They will be sorted then by assessment date as appropriate.

Descriptive summary statistics will be provided in the overall population, by age cohort and body weight group.

In summaries for categorical data all participants in the analysis set will be accounted for with tables displaying the number of participants with missing data. The number and percentage of participants in each category will be tabulated by visit as a shift table against baseline.

Summaries for continuous variables will include basic descriptive statistics: mean, median, first and third quartiles, standard deviation and range (minimum and maximum). Mean and median will be displayed as 1 decimal place more than the individual values. The standard deviations (SDs) will be displayed as 1 additional decimal place beyond that of the mean. If a count is 0, the percentage (0%) should not be displayed. The 0 count will be displayed, but the corresponding percentage should be omitted. If the corresponding denominator for the count is also 0, a hyphen (-) should be displayed rather than a 0 count or NA, and the corresponding percentage should be omitted.

- The participant percentages (%) presented in tables will be 1 decimal place unless the sample sizes for the percentages are small enough to warrant presenting as integers. The standard SAS rounding option will be used. For those percentages that rounds to 0.0, along with the count > 0, we will display < 0.1. For those percentages that would round to 100.0, where the count is less than the denominator, we will display > 99.9.
- All dates to be presented in Date9. format, along with time, wherever applicable.

Handling of Missing or Incomplete Date and Time Fields

Conventions for handling incomplete and missing dates are provided below. ‘Lower limit’ and ‘upper limit’ refer to the minimum or maximum, respectively, of a possible date. For example, if the day is missing, the lowest limit is the first day of the given month and the upper limit is the last day of the given month. If the day and month are missing, the lower limit refers to the 1st January of the given year and the upper limit to the 31st December of the given year.

Type of Date	Date is incomplete	Date is missing
Date of PAH diagnosis	Lower limit	No replacement
AE resolution date	The earlier of the Upper limit and the end of study date	No replacement, considered ongoing at end of study
AE onset date	If the end date of the AE is not before the start of study drug, and if the study drug start falls in the range of possible dates, it is the study drug start date. In all the other cases, it is the lower limit	The earlier of the end date of the AE and the start of study drug
Concomitant medication start date	Lower limit	No replacement, the medication is considered to have started before the study
Concomitant medication end date	The earlier of the Upper limit and the end of treatment date	No replacement, considered ongoing at end of treatment
Death date	Last of the Lower limit and recorded study assessment dates	Last of the recorded study assessment dates

Anomalous information for a date will be handled using the following rules prior to using the imputations mentioned above:

If the day part of a date is non-numeric or has an invalid value, then day will be considered as missing. For example, if date = 44Nov2000 then, as it isn’t possible to have a 44th day of the month, the day will be considered missing.

If the month part of a date does not match that of the possible months, then it will be considered missing, and so will the accompanying day. For example, if date = 21ND99 then both day and month will be considered as missing.

If the year part of a date is non-numeric or has an invalid value, then the whole date will be considered as missing.

General Conventions:

- Study treatments start date is the first day of intake of study treatment. It is derived as the first 'Treatment start date' after sorting in chronological order all records. It coincides with Study Day 1.
- Study treatment end date (EOT) is the last day of intake of study treatment. It is derived as the last 'Treatment end date' after sorting in chronological order all records.
- Starting dose is the dose given on study treatment start date.

Study Day refers to the number of days elapsed since the day of study treatment start, plus 1 (i.e., Study Day 1 is the day of study treatment start). For dates prior to treatment start, it is the negative number of days elapsed between the date under consideration and the day of study treatment start. Therefore, the study day is always different from 0

8. SUPPORTING DOCUMENTATION

8.1. Appendix 1 List of Abbreviations

6MWD	6-minute walk distance
AUC	Area under the plasma concentration-time curve
AUC _{τ,ss}	Area under the plasma concentration-time curve over one dosing interval at steady-state
AUC _{τ,ss,combined}	Combined exposure over one dosing interval at steady-state
C _{max}	Maximum plasma concentration
C _{max,ss}	Maximum concentration at steady state
CHD	Congenital heart disease
CSR	Clinical Study Report
ECG	Electrocardiogram
Echo	Echocardiography
eCRF	electronic Case Report Form
EOS	End-of-Study
EOT	End-of-Treatment
EU	European Union
FAS	Full analysis set
FC	Functional class
GRIPHON	Prostacyclin (PGI ₂ G) receptor agonist in Pulmonary arterial Hypertension
i.v.	Intravenous(ly)
ICF	Informed Consent Form
IDMC	Independent Data Monitoring Committee
iMTD	Individual maximum tolerated dose
LAP	Left atrium pressure
LAR	Legally authorized representative
LVEDP	Left ventricular end-diastolic pressure
MedDRA	Medical Dictionary for Regulatory Activities
mPAP	Mean pulmonary arterial pressure
NT pro-BNP	N-terminal pro b-type natriuretic peptide
NYHA	New York Heart Association
PAH	Pulmonary arterial hypertension
PAWP	Pulmonary arterial wedge pressure
PDE-5	Phosphodiesterase type-5
PK	Pharmacokinetic(s)
PKS	Pharmacokinetic Analysis Set
PT	Preferred term
PVOD	Pulmonary veno-occlusive disease
PVR	Pulmonary vascular resistance
PVRi	Pulmonary vascular resistance index
rhc	Right heart catheterization
SAE	serious adverse event
SAP	Statistical Analysis Plan
SBP	Systolic blood pressure
SD	Standard deviation
SIV	Site initiation visit
SOC	System Organ Class
TEAE	Treatment-emergent adverse event
TESAE	Treatment-emergent serious adverse event
T _{max}	Time at which C _{max} is observed
TSH	Thyroid-stimulating hormone
WHO	World Health Organization

1.1 Anaemia

Cases reporting events of anaemia are retrieved from the safety database for analysis if they contain an event Preferred Term (PT) within the 'Haematopoietic erythropenia' Standardised MedDRA Query (SMQ) (broad scope), or the 'Haematopoietic cytopenias affecting more than one type of blood cell' SMQ (broad scope, with the exception of 2 unspecific PTs: 'blood disorder', 'blood count abnormal'), or if they contain an event with any MedDRA PT containing the text 'anaemia', i.e., any of the following MedDRA PTs:

ANAEMIA
ANAEMIA FOLATE DEFICIENCY
ANAEMIA HEINZ BODY
ANAEMIA MACROCYTIC
ANAEMIA MEGALOBLASTIC
ANAEMIA NEONATAL
ANAEMIA OF CHRONIC DISEASE
ANAEMIA OF MALIGNANT DISEASE
ANAEMIA OF PREGNANCY
ANAEMIA POSTOPERATIVE
ANAEMIA PROPHYLAXIS
ANAEMIA SPLENIC
ANAEMIA VITAMIN B12 DEFICIENCY
ANAEMIA VITAMIN B6 DEFICIENCY
APLASIA PURE RED CELL
APLASTIC ANAEMIA
ASPIRATION BONE MARROW ABNORMAL
AUTOIMMUNE ANAEMIA
AUTOIMMUNE APLASTIC ANAEMIA
AUTOIMMUNE HAEMOLYTIC ANAEMIA
AUTOSOMAL RECESSIVE MEGALOBLASTIC ANAEMIA
BICYTOPENIA
BIOPSY BONE MARROW ABNORMAL
BLOOD INCOMPATIBILITY HAEMOLYTIC ANAEMIA OF NEWBORN
BLOOD LOSS ANAEMIA
BLOOD LOSS ANAEMIA NEONATAL
BONE MARROW DISORDER
BONE MARROW FAILURE
BONE MARROW INFILTRATION
BONE MARROW MYELOGRAM ABNORMAL

BONE MARROW NECROSIS
CARDIAC HAEMOLYTIC ANAEMIA
COLD TYPE HAEMOLYTIC ANAEMIA
CONGENITAL ANAEMIA
CONGENITAL APLASTIC ANAEMIA
CONGENITAL DYSERYTHROPOIETIC ANAEMIA
COOMBS NEGATIVE HAEMOLYTIC ANAEMIA
COOMBS POSITIVE HAEMOLYTIC ANAEMIA
CYTOPENIA
DEFICIENCY ANAEMIA
ERYTHROBLAST COUNT ABNORMAL
ERYTHROBLAST COUNT DECREASED
ERYTHROID MATURATION ARREST
ERYTHROPENIA
ERYTHROPOIESIS ABNORMAL
ERYTHROPOIETIN DEFICIENCY ANAEMIA
FEBRILE BONE MARROW APLASIA
FOETAL ANAEMIA
FULL BLOOD COUNT DECREASED
GELATINOUS TRANSFORMATION OF THE BONE MARROW
HAEMATOCRIT ABNORMAL
HAEMATOCRIT DECREASED
HAEMATOTOXICITY
HAEMOGLOBIN ABNORMAL
HAEMOGLOBIN DECREASED
HAEMOLYTIC ANAEMIA
HAEMOLYTIC ANAEMIA ENZYME SPECIFIC
HAEMOLYTIC ICTEROANAEMIA
HAND AND FOOT SYNDROME SECONDARY TO SICKLE CELL ANAEMIA
HEREDITARY HAEMOLYTIC ANAEMIA
HEREDITARY SIDEROBLASTIC ANAEMIA
HEXOKINASE DEFICIENCY ANAEMIA
HYPERCHROMIC ANAEMIA
HYPOCHROMIC ANAEMIA
HYPOPLASTIC ANAEMIA
IMMUNE-MEDIATED CYTOPENIA
IRON DEFICIENCY ANAEMIA
LEUKOERYTHROBLASTIC ANAEMIA
MELANAEMIA
MICROANGIOPATHIC HAEMOLYTIC ANAEMIA
MICROCYTIC ANAEMIA
MYELODYSPLASTIC SYNDROME
MYELODYSPLASTIC SYNDROME TRANSFORMATION
MYELOFIBROSIS

MYELOID METAPLASIA
 MYELOSUPPRESSION
 NEPHROGENIC ANAEMIA
 NORMOCHROMIC ANAEMIA
 NORMOCHROMIC NORMOCYTIC ANAEMIA
 NORMOCYTIC ANAEMIA
 PANCYTOPENIA
 PANMYELOPATHY
 PERNICIOUS ANAEMIA
 PLASMABLAST COUNT DECREASED
 PRIMARY MYELOFIBROSIS
 PROERYTHROBLAST COUNT ABNORMAL
 PROERYTHROBLAST COUNT DECREASED
 PROTEIN DEFICIENCY ANAEMIA
 PYRUVATE KINASE DEFICIENCY ANAEMIA
 RED BLOOD CELL COUNT ABNORMAL
 RED BLOOD CELL COUNT DECREASED
 REFRACTORY ANAEMIA WITH AN EXCESS OF BLASTS
 REFRACTORY ANAEMIA WITH RINGED SIDEROBLASTS
 RETICULOCYTE COUNT ABNORMAL
 RETICULOCYTE COUNT DECREASED
 RETICULOCYTE PERCENTAGE DECREASED
 RETICULOCYTOPENIA
 SCAN BONE MARROW ABNORMAL
 SICKLE CELL ANAEMIA
 SICKLE CELL ANAEMIA WITH CRISIS
 SIDEROBLASTIC ANAEMIA
 SPHEROCYTIC ANAEMIA
 SPUR CELL ANAEMIA
 WARM TYPE HAEMOLYTIC ANAEMIA

1.2 Bleeding events

Cases including events denoting haemorrhage or GI haemorrhage are retrieved from the safety database for analysis if they contain an event PT within either of the following MedDRA SMQs(narrow scope): ‘Haemorrhage terms (excl. laboratory terms)’, or ‘Gastrointestinal haemorrhage’, i.e., any of the following MedDRA PTs:

ABDOMINAL WALL HAEMATOMA
ABDOMINAL WALL HAEMORRHAGE
ABNORMAL UTERINE BLEEDING
ABNORMAL WITHDRAWAL BLEEDING
ACHENBACH SYNDROME
ACUTE HAEMORRHAGIC LEUKOENCEPHALITIS
ACUTE HAEMORRHAGIC ULCERATIVE COLITIS
ADMINISTRATION SITE BRUISE

ADMINISTRATION SITE HAEMATOMA
ADMINISTRATION SITE HAEMORRHAGE
ADRENAL HAEMATOMA
ADRENAL HAEMORRHAGE
ANAL FISSURE HAEMORRHAGE
ANAL HAEMORRHAGE
ANAL ULCER HAEMORRHAGE
ANASTOMOTIC HAEMORRHAGE
ANASTOMOTIC ULCER HAEMORRHAGE
ANEURYSM RUPTURED
ANGINA BULLOSA HAEMORRHAGICA
ANORECTAL VARICES HAEMORRHAGE
ANTICOAGULANT-RELATED NEPHROPATHY
ANTIPLATELET REVERSAL THERAPY
AORTIC ANEURYSM RUPTURE
AORTIC DISSECTION RUPTURE
AORTIC INTRAMURAL HAEMATOMA
AORTIC PERFORATION
AORTIC RUPTURE
APONEUROSIS CONTUSION
APPLICATION SITE BRUISE
APPLICATION SITE HAEMATOMA
APPLICATION SITE HAEMORRHAGE
APPLICATION SITE PURPURA
ARTERIAL HAEMORRHAGE
ARTERIAL INTRAMURAL HAEMATOMA
ARTERIAL PERFORATION
ARTERIAL RUPTURE
ARTERIOVENOUS FISTULA SITE HAEMATOMA
ARTERIOVENOUS FISTULA SITE HAEMORRHAGE
ARTERIOVENOUS GRAFT SITE HAEMATOMA
ARTERIOVENOUS GRAFT SITE HAEMORRHAGE
ASTRINGENT THERAPY
ATRIAL RUPTURE
AURICULAR HAEMATOMA
BASAL GANGLIA HAEMATOMA
BASAL GANGLIA HAEMORRHAGE
BASILAR ARTERY PERFORATION
BLADDER TAMPONADE
BLEEDING VARICOSE VEIN
BLOOD BLISTER

BLOOD LOSS ANAEMIA
BLOOD URINE
BLOOD URINE PRESENT
BLOODY DISCHARGE
BLOODY PERITONEAL EFFLUENT
BONE CONTUSION
BONE MARROW HAEMORRHAGE
BRAIN CONTUSION
BRAIN STEM HAEMATOMA
BRAIN STEM HAEMORRHAGE
BRAIN STEM MICROHAEMORRHAGE
BREAST HAEMATOMA
BREAST HAEMORRHAGE
BROAD LIGAMENT HAEMATOMA
BRONCHIAL HAEMORRHAGE
BRONCHIAL VARICES HAEMORRHAGE
BULLOUS HAEMORRHAGIC DERMATOSIS
BURSAL HAEMATOMA
CARDIAC CONTUSION
CAROTID ANEURYSM RUPTURE
CAROTID ARTERY PERFORATION
CATHETER SITE BRUISE
CATHETER SITE HAEMATOMA
CATHETER SITE HAEMORRHAGE
CENTRAL NERVOUS SYSTEM HAEMORRHAGE
CEPHALHAEMATOMA
CEREBELLAR HAEMATOMA
CEREBELLAR HAEMORRHAGE
CEREBELLAR MICROHAEMORRHAGE
CEREBRAL ANEURYSM PERFORATION
CEREBRAL ANEURYSM RUPTURED SYPHILITIC
CEREBRAL ARTERIOVENOUS MALFORMATION HAEMORRHAGIC
CEREBRAL ARTERY PERFORATION
CEREBRAL CYST HAEMORRHAGE
CEREBRAL HAEMATOMA
CEREBRAL HAEMORRHAGE
CEREBRAL HAEMORRHAGE FOETAL
CEREBRAL HAEMORRHAGE NEONATAL
CEREBRAL MICROHAEMORRHAGE
CERVIX HAEMATOMA UTERINE
CERVIX HAEMORRHAGE UTERINE

CHEST WALL HAEMATOMA
CHOROIDAL HAEMATOMA
CHOROIDAL HAEMORRHAGE
CHRONIC GASTROINTESTINAL BLEEDING
CHRONIC PIGMENTED PURPURA
CILIARY BODY HAEMORRHAGE
COITAL BLEEDING
COLONIC HAEMATOMA
CONJUNCTIVAL HAEMORRHAGE
CONTUSION
CORNEAL BLEEDING
CULLEN'S SIGN
CYSTITIS HAEMORRHAGIC
DEEP DISSECTING HAEMATOMA
DIARRHOEA HAEMORRHAGIC
DISSEMINATED INTRAVASCULAR COAGULATION
DIVERTICULITIS INTESTINAL HAEMORRHAGIC
DIVERTICULUM INTESTINAL HAEMORRHAGIC
DUODENAL OPERATION
DUODENAL ULCER HAEMORRHAGE
DUODENAL VASCULAR ECTASIA
DUODENITIS HAEMORRHAGIC
EAR HAEMORRHAGE
ECCHYMOSIS
ENCEPHALITIS HAEMORRHAGIC
ENTEROCOLITIS HAEMORRHAGIC
EPIDURAL HAEMORRHAGE
EPISTAXIS
EXSANGUINATION
EXTRA-AXIAL HAEMORRHAGE
EXTRADURAL HAEMATOMA
EXTRADURAL HAEMATOMA EVACUATION
EXTRAVASATION BLOOD
EYE CONTUSION
EYE HAEMATOMA
EYE HAEMORRHAGE
EYELID BLEEDING
EYELID CONTUSION
EYELID HAEMATOMA
FEMORAL ARTERY PERFORATION
FEMORAL VEIN PERFORATION

FOETAL-MATERNAL HAEMORRHAGE
FOTHERGILL SIGN POSITIVE
GASTRIC ANTRAL VASCULAR ECTASIA
GASTRIC HAEMANGIOMA
GASTRIC HAEMORRHAGE
GASTRIC OCCULT BLOOD POSITIVE
GASTRIC ULCER HAEMORRHAGE
GASTRIC ULCER HAEMORRHAGE, OBSTRUCTIVE
GASTRIC VARICES HAEMORRHAGE
GASTRITIS ALCOHOLIC HAEMORRHAGIC
GASTRITIS HAEMORRHAGIC
GASTRODUODENAL HAEMORRHAGE
GASTROINTESTINAL ANASTOMOTIC LEAK
GASTROINTESTINAL ANGIECTASIA
GASTROINTESTINAL HAEMORRHAGE
GASTROINTESTINAL POLYP HAEMORRHAGE
GASTROINTESTINAL ULCER HAEMORRHAGE
GASTROINTESTINAL VASCULAR MALFORMATION HAEMORRHAGIC
GENITAL CONTUSION
GENITAL HAEMORRHAGE
GINGIVAL BLEEDING
GRAFT HAEMORRHAGE
GREY TURNER'S SIGN
HAEMANGIOMA RUPTURE
HAEMARTHROSIS
HAEMATEMESIS
HAEMATOCHYZIA
HAEMATOCOELE
HAEMATOMA
HAEMATOMA EVACUATION
HAEMATOMA INFECTION
HAEMATOMA MUSCLE
HAEMATOSALPINX
HAEMATOSPERMIA
HAEMATOTYMPANUM
HAEMATURIA
HAEMATURIA TRAUMATIC
HAEMOBILIA
HAEMOPERITONEUM
HAEMOPHILIC ARTHROPATHY
HAEMOPHILIC PSEUDOTUMOUR

HAEMOPTYSIS
HAEMORRHAGE
HAEMORRHAGE CORONARY ARTERY
HAEMORRHAGE FOETAL
HAEMORRHAGE IN PREGNANCY
HAEMORRHAGE INTRACRANIAL
HAEMORRHAGE NEONATAL
HAEMORRHAGE SUBCUTANEOUS
HAEMORRHAGE SUBEPIDERMAL
HAEMORRHAGE URINARY TRACT
HAEMORRHAGIC ADRENAL INFARCTION
HAEMORRHAGIC ARTERIOVENOUS MALFORMATION
HAEMORRHAGIC ASCITES
HAEMORRHAGIC BREAST CYST
HAEMORRHAGIC CEREBRAL INFARCTION
HAEMORRHAGIC CYST
HAEMORRHAGIC DIATHESIS
HAEMORRHAGIC DISEASE OF NEWBORN
HAEMORRHAGIC DISORDER
HAEMORRHAGIC EROSIVE GASTRITIS
HAEMORRHAGIC GASTROENTERITIS
HAEMORRHAGIC HEPATIC CYST
HAEMORRHAGIC INFARCTION
HAEMORRHAGIC NECROTIC PANCREATITIS
HAEMORRHAGIC OCCLUSIVE RETINAL VASCULITIS
HAEMORRHAGIC OVARIAN CYST
HAEMORRHAGIC STROKE
HAEMORRHAGIC THYROID CYST
HAEMORRHAGIC TRANSFORMATION STROKE
HAEMORRHAGIC TUMOUR NECROSIS
HAEMORRHAGIC URTICARIA
HAEMORRHAGIC VASCULITIS
HAEMORRHOIDAL HAEMORRHAGE
HAEMOSTASIS
HAEMOTHORAX
HEAVY MENSTRUAL BLEEDING
HENOCH-SCHONLEIN PURPURA
HEPATIC HAEMANGIOMA RUPTURE
HEPATIC HAEMATOMA
HEPATIC HAEMORRHAGE
HEREDITARY HAEMORRHAGIC TELANGIECTASIA

HYPERFIBRINOLYSIS
HYPHAEMA
ILIAC ARTERY PERFORATION
ILIAC ARTERY RUPTURE
ILIAC VEIN PERFORATION
IMMUNE THROMBOCYTOPENIA
IMPLANT SITE BRUISING
IMPLANT SITE HAEMATOMA
IMPLANT SITE HAEMORRHAGE
INCISION SITE HAEMATOMA
INCISION SITE HAEMORRHAGE
INCREASED TENDENCY TO BRUISE
INDUCED ABORTION HAEMORRHAGE
INFERIOR VENA CAVA PERFORATION
INFUSION SITE BRUISING
INFUSION SITE HAEMATOMA
INFUSION SITE HAEMORRHAGE
INJECTION SITE BRUISING
INJECTION SITE HAEMATOMA
INJECTION SITE HAEMORRHAGE
INSTILLATION SITE BRUISE
INSTILLATION SITE HAEMATOMA
INSTILLATION SITE HAEMORRHAGE
INTERMENSTRUAL BLEEDING
INTERNAL HAEMORRHAGE
INTESTINAL HAEMATOMA
INTESTINAL HAEMORRHAGE
INTESTINAL VARICES HAEMORRHAGE
INTRA-ABDOMINAL HAEMATOMA
INTRA-ABDOMINAL HAEMORRHAGE
INTRACEREBRAL HAEMATOMA EVACUATION
INTRACRANIAL HAEMATOMA
INTRACRANIAL TUMOUR HAEMORRHAGE
INTRAOCULAR HAEMATOMA
INTRAPARTUM HAEMORRHAGE
INTRATUMOURAL HAEMATOMA
INTRAVENTRICULAR HAEMORRHAGE
INTRAVENTRICULAR HAEMORRHAGE NEONATAL
IRIS HAEMORRHAGE
JOINT MICROHAEMORRHAGE
JUGULAR VEIN HAEMORRHAGE

KIDNEY CONTUSION
LACRIMAL HAEMORRHAGE
LARGE INTESTINAL HAEMORRHAGE
LARGE INTESTINAL ULCER HAEMORRHAGE
LARYNGEAL HAEMATOMA
LARYNGEAL HAEMORRHAGE
LIP HAEMATOMA
LIP HAEMORRHAGE
LIVER CONTUSION
LOWER GASTROINTESTINAL HAEMORRHAGE
LOWER LIMB ARTERY PERFORATION
LYMPH NODE HAEMORRHAGE
MALLORY-WEISS SYNDROME
MEDIASTINAL HAEMATOMA
MEDIASTINAL HAEMORRHAGE
MEDICAL DEVICE SITE BRUISE
MEDICAL DEVICE SITE HAEMATOMA
MEDICAL DEVICE SITE HAEMORRHAGE
MELAENA
MELAENA NEONATAL
MENINGORRHAGIA
MENOMETRORRHAGIA
MESENTERIC HAEMATOMA
MESENTERIC HAEMORRHAGE
MOUTH HAEMORRHAGE
MUCOCUTANEOUS HAEMORRHAGE
MUCOSAL HAEMORRHAGE
MUSCLE CONTUSION
MUSCLE HAEMORRHAGE
MYOCARDIAL HAEMORRHAGE
MYOCARDIAL RUPTURE
NAEVUS HAEMORRHAGE
NAIL BED BLEEDING
NASAL SEPTUM HAEMATOMA
NEONATAL GASTROINTESTINAL HAEMORRHAGE
NEPHRITIS HAEMORRHAGIC
NIPPLE EXUDATE BLOODY
OCCULT BLOOD POSITIVE
OCULAR RETROBULBAR HAEMORRHAGE
OESOPHAGEAL HAEMORRHAGE
OESOPHAGEAL INTRAMURAL HAEMATOMA

OESOPHAGEAL ULCER HAEMORRHAGE
OESOPHAGEAL VARICES HAEMORRHAGE
OESOPHAGITIS HAEMORRHAGIC
OMENTAL HAEMORRHAGE
OPTIC DISC HAEMORRHAGE
OPTIC NERVE SHEATH HAEMORRHAGE
ORAL BLOOD BLISTER
ORAL CONTUSION
ORAL MUCOSA HAEMATOMA
ORAL PURPURA
ORBITAL HAEMATOMA
ORBITAL HAEMORRHAGE
OSTEORRHAGIA
OVARIAN HAEMATOMA
OVARIAN HAEMORRHAGE
PALPABLE PURPURA
PANCREATIC HAEMORRHAGE
PANCREATIC PSEUDOCYST HAEMORRHAGE
PANCREATITIS HAEMORRHAGIC
PAPILLARY MUSCLE HAEMORRHAGE
PARANASAL SINUS HAEMATOMA
PARANASAL SINUS HAEMORRHAGE
PARATHYROID HAEMORRHAGE
PAROTID GLAND HAEMORRHAGE
PELVIC HAEMATOMA
PELVIC HAEMATOMA OBSTETRIC
PELVIC HAEMORRHAGE
PENILE CONTUSION
PENILE HAEMATOMA
PENILE HAEMORRHAGE
PEPTIC ULCER HAEMORRHAGE
PERICARDIAL HAEMORRHAGE
PERINEAL HAEMATOMA
PERIORBITAL HAEMATOMA
PERIORBITAL HAEMORRHAGE
PERIOSTEAL HAEMATOMA
PERIPARTUM HAEMORRHAGE
PERIPHERAL ARTERY ANEURYSM RUPTURE
PERIPHERAL ARTERY HAEMATOMA
PERITONEAL HAEMATOMA
PERIVENTRICULAR HAEMORRHAGE NEONATAL

PETECHIAE
PHARYNGEAL CONTUSION
PHARYNGEAL HAEMATOMA
PHARYNGEAL HAEMORRHAGE
PITUITARY APOPLEXY
PITUITARY HAEMORRHAGE
PLACENTA PRAEVIA HAEMORRHAGE
POLYMENORRHAGIA
POST ABORTION HAEMORRHAGE
POST PROCEDURAL CONTUSION
POST PROCEDURAL HAEMATOMA
POST PROCEDURAL HAEMATURIA
POST PROCEDURAL HAEMORRHAGE
POST TRANSFUSION PURPURA
POST-TRAUMATIC PUNCTATE INTRAEPIDERMAL HAEMORRHAGE
POSTMENOPAUSAL HAEMORRHAGE
POSTPARTUM HAEMORRHAGE
PREMATURE SEPARATION OF PLACENTA
PROCEDURAL HAEMORRHAGE
PROCTITIS HAEMORRHAGIC
PROSTATIC HAEMORRHAGE
PULMONARY ALVEOLAR HAEMORRHAGE
PULMONARY CONTUSION
PULMONARY HAEMATOMA
PULMONARY HAEMORRHAGE
PULMONARY HAEMORRHAGE NEONATAL
PUNCTURE SITE BRUISE
PUNCTURE SITE HAEMATOMA
PUNCTURE SITE HAEMORRHAGE
PURPURA
PURPURA FULMINANS
PURPURA NEONATAL
PURPURA NON-THROMBOCYTOPENIC
PURPURA SENILE
PUTAMEN HAEMORRHAGE
RADIATION ASSOCIATED HAEMORRHAGE
RECTAL HAEMORRHAGE
RECTAL ULCER HAEMORRHAGE
RENAL ARTERY PERFORATION
RENAL CYST HAEMORRHAGE
RENAL HAEMATOMA

RENAL HAEMORRHAGE
RESPIRATORY TRACT HAEMORRHAGE
RESPIRATORY TRACT HAEMORRHAGE NEONATAL
RETINAL ANEURYSM RUPTURE
RETINAL HAEMORRHAGE
RETINOPATHY HAEMORRHAGIC
RETROPERITONEAL HAEMATOMA
RETROPERITONEAL HAEMORRHAGE
RETROPLACENTAL HAEMATOMA
RUPTURED CEREBRAL ANEURYSM
SCLERAL HAEMATOMA
SCLERAL HAEMORRHAGE
SCROTAL HAEMATOCOELE
SCROTAL HAEMATOMA
SCROTAL HAEMORRHAGE
SHOCK HAEMORRHAGIC
SKIN HAEMORRHAGE
SKIN NEOPLASM BLEEDING
SKIN ULCER HAEMORRHAGE
SMALL INTESTINAL HAEMORRHAGE
SMALL INTESTINAL ULCER HAEMORRHAGE
SOFT TISSUE HAEMORRHAGE
SPERMATIC CORD HAEMORRHAGE
SPINAL CORD HAEMATOMA
SPINAL CORD HAEMORRHAGE
SPINAL EPIDURAL HAEMATOMA
SPINAL EPIDURAL HAEMORRHAGE
SPINAL SUBARACHNOID HAEMORRHAGE
SPINAL SUBDURAL HAEMATOMA
SPINAL SUBDURAL HAEMORRHAGE
SPLEEN CONTUSION
SPLENIC ARTERY PERFORATION
SPLENIC HAEMATOMA
SPLENIC HAEMORRHAGE
SPLENIC VARICES HAEMORRHAGE
SPLINTER HAEMORRHAGES
SPONTANEOUS HAEMATOMA
SPONTANEOUS HAEMORRHAGE
STOMA SITE HAEMORRHAGE
STOMATITIS HAEMORRHAGIC
SUBARACHNOID HAEMATOMA

SUBARACHNOID HAEMORRHAGE
SUBARACHNOID HAEMORRHAGE NEONATAL
SUBCAPSULAR HEPATIC HAEMATOMA
SUBCAPSULAR RENAL HAEMATOMA
SUBCAPSULAR SPLENIC HAEMATOMA
SUBCHORIONIC HAEMATOMA
SUBCHORIONIC HAEMORRHAGE
SUBCLAVIAN ARTERY PERFORATION
SUBCLAVIAN VEIN PERFORATION
SUBCUTANEOUS HAEMATOMA
SUBDURAL HAEMATOMA
SUBDURAL HAEMATOMA EVACUATION
SUBDURAL HAEMORRHAGE
SUBDURAL HAEMORRHAGE NEONATAL
SUBENDOCARDIAL HAEMORRHAGE
SUBGALEAL HAEMATOMA
SUBGALEAL HAEMORRHAGE
SUBRETINAL HAEMATOMA
SUPERIOR VENA CAVA PERFORATION
TESTICULAR HAEMORRHAGE
THALAMUS HAEMORRHAGE
THIRD STAGE POSTPARTUM HAEMORRHAGE
THORACIC HAEMORRHAGE
THROMBOCYTOPENIC PURPURA
THROMBOTIC THROMBOCYTOPENIC PURPURA
THYROID HAEMORRHAGE
TONGUE HAEMATOMA
TONGUE HAEMORRHAGE
TONSILLAR HAEMORRHAGE
TOOTH PULP HAEMORRHAGE
TOOTH SOCKET HAEMORRHAGE
TRACHEAL HAEMORRHAGE
TRAUMATIC HAEMATOMA
TRAUMATIC HAEMORRHAGE
TRAUMATIC HAEMOTHORAX
TRAUMATIC INTRACRANIAL HAEMATOMA
TRAUMATIC INTRACRANIAL HAEMORRHAGE
TUMOUR HAEMORRHAGE
ULCER HAEMORRHAGE
UMBILICAL CORD HAEMORRHAGE
UMBILICAL HAEMATOMA

UMBILICAL HAEMORRHAGE
UPPER GASTROINTESTINAL HAEMORRHAGE
URETERIC HAEMORRHAGE
URETHRAL HAEMORRHAGE
URINARY BLADDER HAEMATOMA
URINARY BLADDER HAEMORRHAGE
URINARY OCCULT BLOOD
URINARY OCCULT BLOOD POSITIVE
UROGENITAL HAEMORRHAGE
UTERINE HAEMATOMA
UTERINE HAEMORRHAGE
VACCINATION SITE BRUISING
VACCINATION SITE HAEMATOMA
VACCINATION SITE HAEMORRHAGE
VAGINAL HAEMATOMA
VAGINAL HAEMORRHAGE
VARICOSE VEIN RUPTURED
VASCULAR ACCESS SITE BRUISING
VASCULAR ACCESS SITE HAEMATOMA
VASCULAR ACCESS SITE HAEMORRHAGE
VASCULAR ACCESS SITE RUPTURE
VASCULAR ANASTOMOTIC HAEMORRHAGE
VASCULAR GRAFT HAEMORRHAGE
VASCULAR PSEUDOANEURYSM RUPTURED
VASCULAR PURPURA
VASCULAR RUPTURE
VEIN RUPTURE
VENOUS HAEMORRHAGE
VENOUS PERFORATION
VENTRICLE RUPTURE
VERTEBRAL ARTERY PERFORATION
VESSEL PUNCTURE SITE BRUISE
VESSEL PUNCTURE SITE HAEMATOMA
VESSEL PUNCTURE SITE HAEMORRHAGE
VITREOUS HAEMATOMA
VITREOUS HAEMORRHAGE
VULVAL HAEMATOMA
VULVAL HAEMATOMA EVACUATION
VULVAL HAEMORRHAGE
WHITE NIPPLE SIGN
WITHDRAWAL BLEED

WOUND HAEMATOMA

WOUND HAEMORRHAGE

1.3 Gastrointestinal disturbances denoting intestinal intussusception (manifested as ileus or obstruction)

Cases including events denoting GI disturbances are retrieved from the safety database for analysis if they contain an event with any MedDRA PT containing the text ‘ileus’, ‘intestinal obstruction’, ‘intestinal pseudo-obstruction’, ‘intussusception’, or ‘volvulus’, with the exception of unspecific PT: ‘keratomileusis’, i.e., any of the following MedDRA PTs:

CONGENITAL INTESTINAL OBSTRUCTION
DISTAL INTESTINAL OBSTRUCTION SYNDROME
GALLBLADDER VOLVULUS
GALLSTONE ILEUS
GASTRIC ILEUS
GASTRIC VOLVULUS
GASTROINTESTINAL OBSTRUCTION
ILEUS
ILEUS PARALYTIC
ILEUS SPASTIC
INTESTINAL OBSTRUCTION
INTESTINAL PSEUDO-OBSTRUCTION
INTUSSUSCEPTION
LARGE INTESTINAL OBSTRUCTION
LARGE INTESTINAL OBSTRUCTION REDUCTION
MALIGNANT GASTROINTESTINAL OBSTRUCTION
MECHANICAL ILEUS
MECONIUM ILEUS
NEONATAL INTESTINAL OBSTRUCTION
POSTOPERATIVE ILEUS
SMALL INTESTINAL INTUSSUSCEPTION REDUCTION
SMALL INTESTINAL OBSTRUCTION
SMALL INTESTINAL OBSTRUCTION REDUCTION
SUBILEUS
VOLVULUS
VOLVULUS OF SMALL BOWEL
VOLVULUS REPAIR

